## 3.6.4 Visit 4: Assessments immediately after anaesthesia induction

- If relevant bronchopulmonary aspiration is suspected, it needs to be confirmed by bronchoscopy or radiology imaging up to 48 h after anaesthesia procedure. In that case the patient will be monitored for an additional 48 h and the outcome will be documented in the eCRF and the AE/SAE section if applicable. The sponsor is to be informed of every instance of confirmed bronchopulmonary aspiration within 24 h even if the SAE criteria are not met. The risk/benefit consideration has to be revaluated.
- Vital signs including heart rate and blood pressure will be collected from the routine data. The lowest value 15 min after anaesthesia induction will be documented.
- If not already done, a blood sample for glucose levels is to be drawn.

## 3.6.5 Visit 5: Assessments at follow up (2 h ± 30 min after procedure)

Follow up takes place  $2 h \pm 30$  min after the procedure. For general anaesthesia this is 2 h after extubation. For regional anaesthesia this is 2 h after skin suture.

CAM-ICU is a well validated score that has been used in the awakening ward setting to detect immediate onset delirium^62. As described in "CAM-ICU Training Manual and FAQ", the CAM-ICU is not applicable if RASS is -4 oder -5.

If CAM-ICU is negative, the Bauer satisfaction questionnaire will be obtained with all items and the item "Headache".

If CAM-ICU is positive or indeterminable, the Bauer satisfaction questionnaire is considered indeterminable. Sicker patients being missing from the data might skew the data (Attrition-Bias).

An indeterminable Bauer satisfaction questionnaire will therefore be repeated on POD1. PONV for up to 2 hours will be documented in the following dimensions: Vomiting, retching, nausea, and/or use of rescue medication.

The safety endpoints and feasibility assessments will be considered present if they occurred before the end of the last Visit.

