Study Procedures	Group 1 (control) - Usual care: Fasting instructions as given by anaesthesiologist according to national guidelines (6 h solid meal and thick liquids, 2 h clear fluids).  Group 2 (intervention) - Instructed guideline adherence: As per "Usual care". In addition, the operating room schedule is closely monitored and the patient will be visited to be supported and encouraged in drinking clear fluids freely until 2 h before the anticipated beginning of anaesthesia.  Group 3 (intervention) - Experimental intervention: As per "instructed guideline adherence" with the difference that the patient will be educated and encouraged to drink up to 200 ml clear fluids between 2 h prior to anaesthesia and the call to operation room. From this concludes that patients are allowed to drink up to 100 ml clear fluids every 1 h the anaesthesia is postponed.  Follow-up per patient: 2 h after discharge from the operating room (up to 48 h e.g. in case of bronchopulmonary aspiration).
Biometry	Analyses will be intention-to-treat. The primary endpoint will be analysed by standard methods of descriptive statistics, namely chisquare test.  The treatment effect will be quantified on the odds ratio scale with two-sided 95% confidence intervals provided. Secondarily, also point estimates and confidence intervals for the rate difference and the relative risk will be provided.  The overall trial will have 80% power (alpha=0.05)

Trial Duration	Duration of intervention: On the day of scheduled surgery until call to the operating room.
	Individual trial duration: From the day of scheduled surgery until up to 2 h after discharge from the operating room. Follow-up might be postponed up to 48 h e.g. in case of bronchopulmonary aspiration.
	Planned recruitment period: 3 months
	The trial formally starts with the treatment of the first patient (FPI = first patient in), and the formal end of the study is the last follow-up visit of the last patient included (LPO = last patient out). The total study duration will be 3 months.

[figure not shown]

Fig. 1: Possible courses through the study

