## 1.2.1 Schedule of Assessments and Procedures

Examinations	Screening	Intervention	Prior to anaesthesia	After induction	Follow up
	28 days up to 0 days before surgery	On the day of surgery until call to the operating room	Immediately before anaesthesia induction	Immediately after anaesthesia induction	2 h (±30 min) after procedure a
Visit	V1	V2	V3	V4	V5
Inclusion criteria	X				
Exclusion criteria	X				
Informed consent	X				
Medical history b Baseline	Х				
assessments	х				
Registration	X				
Demographics	X				
Randomisation	Х				
Intervention		X			
Fasting time			(X) c		Х
IV-catheter placement			x		
Patient satisfaction			Х		Х
Blood glucose level			Х	(X) d	
Vital signs			Х	Х	
Use of vasopressors				Х	
Bronchopulmonary aspiration				X	X
Headache			X	^	X
PONV					X
RASS + CAM-ICU					X
Blinding successful			Х	Х	Х

<sup>aFor general anaesthesia this is 2 h after extubation. For regional anaesthesia this is 2 h after skin suture. Parts of Follow up might be postponed up to 48 h e.g. if bronchopulmonary aspiration is to be confirmed.

<sup>bThe premedication visit will be added to the study documentation to record the inclusion and exclusion criteria.

<sup>cFluid fasting time must be greater than 30 minutes at anaesthesia induction. The actual fasting time will be assessed at the end of V5 to ensure outcome assessor blinding. dOnly if not done at V4.

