#### 3.2.1 Inclusion criteria

Patients may only be allowed to drink clear fluids up to call to operating room if they fulfill all the following criteria:

- 1. Adult patients (≥ 18 years)
- 2. Undergoing surgery under anaesthesia care: general anaesthesia, regional anaesthesia, combined anaesthesia or monitored anaesthesia care.
- 3. ASA physical status classification I-III

The proportion of patients undergoing general or combined anaesthesia is aimed to exceed 75%.

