## Safety Endpoints:

- 10. Unplanned postoperative admission to an intermediate care unit (IMC) or intensive care unit (ICU) due to respiratory insufficiency.
- 11. Confirmed Bronchopulmonary aspiration
- 12. Death within observation period

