# 3.6 Participant Timeline and Individual Study Visits

Follow-up per patient: Until completion of the last Visit (regularly 2 h ± 30 min after procedure, up to 48 h after procedure if e.g. bronchopulmonary aspiration is suspected.)

Duration of intervention per patient: From randomisation until call to the operating room.

Informed Consent, inclusion and withdrawal from the study is handled according to ICH-GCP.

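### Read together, sections 3.6 and 3.6.5 count respiratory IMC/ICU admission and death over a longer period in patients with suspected aspiration than in the rest

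*Combined protocol and SAP*

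**What the plan says.** Section 3.5.2 lists three safety endpoints: unplanned IMC or ICU admission for respiratory insufficiency, confirmed bronchopulmonary aspiration, and "Death within observation period". It gives admission no time window and does not say how long the observation period is.

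The only counting rule is in 3.6.5: "The safety endpoints and feasibility assessments will be considered present if they occurred before the end of the last Visit". Section 3.6 places the last visit at 2 h ± 30 min after the procedure as a rule, but "up to 48 h after procedure if e.g. bronchopulmonary aspiration is suspected". Footnote a of the schedule (1.2.1) is narrower: "Parts of Follow up might be postponed up to 48 h e.g. if bronchopulmonary aspiration is to be confirmed".

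The start of the 2 h also varies. The Synopsis gives the individual trial duration as "From the day of scheduled surgery until up to 2 h after discharge from the operating room", again with a possible postponement to 48 h. Section 3.6.5, like 1.2.1, says: "For general anaesthesia this is 2 h after extubation. For regional anaesthesia this is 2 h after skin suture". Section 3.2.1 admits "general anaesthesia, regional anaesthesia, combined anaesthesia or monitored anaesthesia care", so monitored anaesthesia care is eligible but has no start point.

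Two further passages bear on when follow-up ends. Section 3.6.4 provides for an additional 48 h of monitoring in the aspiration work-up. Section 3.6.5 repeats an indeterminable questionnaire on the first postoperative day, without saying whether this moves the last visit.

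**The concern.** The event that lengthens follow-up is related to the endpoints being counted. Suppose two patients are each admitted to intensive care for respiratory insufficiency 20 h after surgery. If aspiration had been suspected in the first, the last visit may not yet have ended and the admission counts. If the second had an uneventful visit at 2 h, the same admission does not count. Counting time then depends on early outcome.

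Admission and death are two of the three safety endpoints. A table of counts per arm would mix unequal observation periods, and a zero would mostly describe the time through surgery to about 2 h afterwards. Anyone using the pilot's safety counts to plan a larger trial would need to know which period they cover.

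**Working it through.** **Denominators.** The plan states no figure for the safety endpoints. Its group size reproduces: 55 / 0.95 = 57.9, rounded up to 58 per group, and 3 × 58 = 174 (section 5.5 and its drop-out paragraph).

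**Passages side by side.**

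| Section | End of counting or follow-up | Same for all patients? |
|---|---|---|
| 3.6.5 | End of the last visit | Only if the last visit is |
| 3.6 | 2 h ± 30 min; up to 48 h if e.g. aspiration is suspected | No |
| 1.2.1, footnote a | 2 h ± 30 min; parts may be postponed up to 48 h | Unclear which parts |
| 1.2 Synopsis | 2 h after operating-room discharge; may be postponed up to 48 h | No |
| 3.5.2 | Observation period (death); none given (admission) | Not fixed |

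As far as the tables can be read, neither the schedule (1.2.1) nor the follow-up list in the flow chart (1.2.2) has a line for admission or death. They therefore do not settle which parts may be postponed.

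**Length of the windows.** The regular visit falls 1.5 to 2.5 h after the procedure. Against 48 h the ratio is 48 / 2.5 = 19.2 to 48 / 1.5 = 32.

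**Scale, on assumptions only.** None of these three quantities is in the documents:

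- r: risk of the event over a fixed 48 h window;
- L: share of those events that fall after Visit 5;
- f: share of the late events that occur in patients whose follow-up was extended, and so are counted.

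Share counted = 1 − L(1 − f). Events uncounted in 174 = 174 × r × L × (1 − f). Chance of zero counted events in an arm of 58 = (1 − r × share counted)^58.

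With L = f = 0.5 the share counted is 0.75. With each taken from 0.25 to 0.75, it runs from 0.4375 (L = 0.75, f = 0.25) to 0.9375 (L = 0.25, f = 0.75). At r = 1% this gives 174 × 0.01 × 0.25 = 0.435 events uncounted, and (1 − 0.0075)^58 = 0.646 against 0.99^58 = 0.558.

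| r | Expected in 174 | Uncounted (range) | Zero in 58, current rule (range) | Zero in 58, fixed 48 h |
|---|---|---|---|---|
| 0.1% | 0.17 | 0.04 (0.01 to 0.10) | 96% (95% to 97%) | 94% |
| 1% | 1.74 | 0.44 (0.11 to 0.98) | 65% (58% to 78%) | 56% |
| 5% | 8.7 | 2.2 (0.5 to 4.9) | 11% (6% to 28%) | 5% |

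**How far the assumptions drive this.** Two cases outside the range, both at r = 1%:

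- If nearly all late events follow a suspected aspiration (L = 0.5, f = 0.95), the loss is 174 × 0.01 × 0.5 × 0.05 = 0.04.
- If the hazard is constant over 48 h, a 2 h window holds [1 − 0.99^(2/48)] / 0.01 = 4.2% of the events. With nobody extended, the loss is 1.74 × 0.958 = 1.67.

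The answer moves from 0.04 to 1.67 of 1.74 events, so the documents do not determine it.

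**What a zero can show.** Zero events in 58 excludes, one-sided at 95%, only risks above 1 − 0.05^(1/58) = 5.0%. No choice of window changes that.

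**The case against.** *There is already a common window.* Visit 5 is scheduled at the same time for every patient, one rule covers all three arms, and footnote a postpones only parts of follow-up, with aspiration confirmation as its example. On that reading admission and death stop at Visit 5 for everyone. The reading is fair, so it cannot be said that the counts will necessarily mix windows. But 3.6.5 refers to the last visit, 3.6 lets that visit move, and no passage exempts these two endpoints.

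*The extension catches the events that matter.* An admission caused by aspiration would usually follow a suspected aspiration, so f may be well above one half and the loss close to nil. This stands for aspiration-related events. It does not cover other respiratory admissions or deaths.

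*Late events are lost altogether.* A reader might infer this, but the documents do not support it. Section 6.1.1 gives adverse events no end time, 6.1.2 makes death and prolonged hospitalisation serious, and 6.2 requires safety outcomes that meet the definition to be documented. A late event may well be recorded. What is missing is a rule that makes it count as an endpoint, or a look after the last visit.

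*The arms are biased.* This is also tempting, because section 4.2 accepts that the attending anaesthetist can be unblinded and suspicion could then vary by arm. Nothing in the documents shows that it would, and outcome assessors are to be kept blinded.

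*No decision rests on these counts.* There is no safety hypothesis, safety test or count-based stopping rule, and section 6 says that immediate safety is not the primary focus. This stands and limits the weight of the point. The same section still names the safety endpoints as data of special interest.

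**Conclusion.** The point holds as a defect in the counting rule. Sections 3.6 and 3.6.5, followed as written, give respiratory admission and death a counting period that depends on an early, endpoint-related sign. The Synopsis, 1.2.1, 3.5.2 and the adverse-event sections set no common cut-off that overrides this.

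The size cannot be determined, because risk, timing and the share of late events in extended patients are all assumed above. At low risk the effect is likely small, and the 5% row only marks an upper end. The table should not be read as an estimate of events this trial will miss. The thirst analysis and sample size are untouched, and 58 per arm cannot establish safety under any window. This is a cheap improvement to safety reporting in a pilot and worth making.

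**What to change.** In 3.5.2 and 3.6.5, state one counting period for the two endpoints. A minimum wording:

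> Unplanned respiratory IMC/ICU admission and death are counted from the start of the intervention period on the day of surgery to the scheduled Visit 5, in every patient of all three arms, whatever the suspicion of aspiration, the CAM-ICU result or the repeat questionnaire. This is the observation period for death. Later events are listed separately by arm. For counting, only confirmation of aspiration uses the extension to 48 h.

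Name the day of surgery explicitly, because 3.6 dates the intervention from randomisation while the Synopsis dates it from the day of surgery. This version needs no record check. Its downside is that the counts describe only the short window.

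Optionally, also tabulate both endpoints to a fixed later time, such as 48 h, from the hospital record, with the number of incomplete records per arm. That costs one record check and one eCRF field for each of 174 patients. It will be incomplete for outpatients, who are enrolled (3.1), since 5.2 relies on follow-up ending before discharge. It may also need ethics re-appraisal under 7.3 if the patient information or consent form has to change. Reporting per arm how many patients had follow-up extended would show whether the extension was used unevenly.

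Two sets of passages must be reconciled:

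- the start of the 2 h: operating-room discharge in the Synopsis, extubation or skin suture in 1.2.1 and 3.6.5, nothing named for monitored anaesthesia care;
- the limit of up to 48 h in the Synopsis, 1.2.1 and 3.6, against the additional 48 h in 3.6.4.

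All of this concerns how events are counted, not how patients are monitored.

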## 3.6.6 Premature Termination of the Intervention Phase for Individual Patients

The trial intervention phase may be terminated prematurely in case of:

- 1. Eligibility criteria are not met.
- 2. At the judgement of the investigator for any other reason of medical prudence.
- 3. On request of the patient.

In case of premature termination of intervention phase, it is necessary to document the reason of termination and the current condition of the patient.

## 3.6.7 Plan for Further Treatment

Patients will be treated as usual after the individual treatment period of the clinical trial.

## 4 METHODS: ASSIGNMENT OF INTERVENTIONS

## 4.1 Allocation

Sequence Generation: Patients will be randomly assigned to either control or experimental group with a 1:1 allocation per computer generated randomisation schedule using permuted blocks of random sizes. The block sizes will not be disclosed.

Concealment Mechanism: Patients will be randomised using a web-based randomisation system (embedded in REDCap). Allocation concealment will be ensured.

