# 1.2 Synopsis

Title	A pilot study to test benefits of drinking clear fluids until called to the operating room in adult surgical patients.		
Short title	HYDRATE-Study		
Indication	Patients ≥ 18 years of age undergoing surgery without an indication for rapid sequence induction.		
Primary end point	
 
Primary efficacy endpoint:
 
Patient thirst (No; Yes, moderate; Yes, severe)
 
Endpoint will be measured prior to anaesthesia induction.
 
		
Secondary end points	Endpoint will be measured prior to anaesthesia induction.  Key secondary endpoints:  We will pilot test the intervention to demonstrate its acceptability and feasibility and to identify target outcomes for further trials.  Piloting for feasibility assessment:  Total number of protocol deviations per group  Outcome assessment successfully blinded  Real fluid fasting time is less than allocated fluid fasting time  Fluid fasting time		

	Piloting for future power calculations: Richmond Agitation Sedation Scale (RASS) Confusion Assessment Method for the Intensive Care Unit (CAM-ICU) Headache Vital signs (delta heart rate, delta blood pressure) Cumulative Vasopressor dose within 15 min after anaesthesia induction Blood glucose level Number of attempts for placing a peripheral intravenous catheter Postoperative nausea and vomiting (PONV)  Safety Endpoints: Unplanned intensive/intermediate care unit stay due to respiratory complications
	

Confirmed bronchopulmonary aspiration

Death within observation period

Trial design	The study is a prospective, single centre, outcome assessor
Trial population	blinded, controlled randomised clinical trial (RCT) with 3 arms.  Inclusion criteria on the individual level: Patients ≥ 18 years of age scheduled for surgery under anaesthesia care (general anaesthesia, regional anaesthesia, combined anaesthesia or monitored anaesthesia care) with an ASA physical status classification I-III.  Exclusion criteria: Absolute and relative indication for rapid sequence induction, dysphagia, renal replacement therapy, fluid restriction therapy, pregnancy, expected need for postoperative mechanical ventilation and prior enrolment in this trial.
Sample size	n = 174 (55 per group +5% drop-outs = 58 per group)

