# 2.4 Trial design

#### 2.4.1 Trial Design

The study is an outcome assessor blinded randomised trial (RCT) with three parallel treatment arms.

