# 5.5 Sample Size

We plan randomising n=174 patients. n = 174 (55 per group +5% Dropout)

The primary endpoint of this study is thirst immediately before anaesthesia induction. For this purpose, the Bauer Satisfaction Questionnaire is dichotomised - "yes (moderate or strong)" vs. "no thirst". The three groups will be compared with each other. In the control group, based on Bauer et al, 2001, a value of 53% is assumed based on our own experience it is assumed that the experimental intervention (group 3) has a relative effect of 50% and therefore only 26.5% of patients are still thirsty. For group 2 (Instructed guideline adherence) a somewhat weaker effect is assumed. We assume that thirst can be reduced to 30% in this group.

In order to detect these differences between all three groups using a Chi² test with a power of 80%, a total of 165 patients is needed - 55 patients per group.

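### Section 4.1 allocates patients to two groups at 1:1, while every other section describes and sizes three equal arms; the allocation text should state three groups at 1:1:1

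*Combined protocol and SAP*

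**What the plan says.** Section 4.1 (Allocation), under sequence generation, states that patients will be "randomly assigned to either control or experimental group with a 1:1 allocation", from a computer-generated schedule in permuted blocks of random, undisclosed sizes. No other section gives a ratio. Section 3.6.1 describes the REDCap randomisation step but mentions neither the number of arms nor a ratio.

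The rest of the document has three arms:

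- The synopsis (1.2) calls the study a "controlled randomised clinical trial (RCT) with 3 arms" and gives the size as "n = 174 (55 per group +5% drop-outs = 58 per group".
- The flow chart (1.2.2) leads from randomisation to Groups 1, 2 and 3.
- Section 2.4.1 describes a trial "with three parallel treatment arms".
- Section 3.2 defines three procedures. Group 1 is labelled control, Group 2 intervention (instructed guideline adherence) and Group 3 intervention (experimental intervention).
- Section 5.5 says "The three groups will be compared with each other" and concludes that "a total of 165 patients is needed - 55 patients per group". Its drop-out paragraph raises this to 58 per group.

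**The concern.** The allocation paragraph is operative text: the randomisation table is built from it, and an ethics committee, a monitor or a later reader checks the trial against it. Here it names two groups and gives a two-term ratio for a three-arm trial. The two names it uses match the labels of Group 1 (control) and Group 3 (experimental) in 3.2, and Group 2 has no clear place in the sentence.

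A table built from the sentence as it stands would not yield the three equal arms that were sized, and this could not be undone for patients already randomised. There is also a formal oddity. Section 8.1 counts any departure from the procedures in the document as a protocol violation, so a correct 1:1:1 table would, read strictly, depart from 4.1.

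**Working it through.** **Inputs.** Thirst rates of 53%, 30% and 26.5% for Groups 1, 2 and 3, a chi-square test, 80% power, 55 evaluable per group (165) and 5% drop-out come from 5.5. Alpha of 0.05 comes from the synopsis (Biometry).

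**Step 1: reproduce the plan's figure with three equal arms.**

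- Mean rate = (0.53 + 0.30 + 0.265)/3 = 0.365.
- Squared deviations: 0.165² + 0.065² + 0.100² = 0.04145.
- w² = (0.04145/3)/(0.365 × 0.635) = 0.0596.
- Non-centrality λ = N·w² = 165 × 0.0596 = 9.84, with 2 degrees of freedom.
- Power = 0.809 (simulation 0.808). The smallest size reaching 80% is 54 per group, so 55 reproduces.
- Drop-out: 55/0.95 = 57.9, rounded up to 58; 3 × 58 = 174.

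The stated size therefore rests on 1:1:1 allocation and is correct on that basis.

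**Step 2: read 4.1 literally (control or experimental, 1:1).**

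- 174/2 = 87 in each of Groups 1 and 3, and none in Group 2.
- The three-group test in 5.5 cannot be computed. A two-group comparison of 53% with 26.5% at 87 per arm would have power 0.953, but that is a different trial.

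**Step 3: assume Groups 2 and 3 share the experimental half equally.** The text does not state this split.

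- Allocation is 2:1:1: 87/43.5/43.5 of 174 randomised, or about 82/41/42 of 165 evaluable.
- Mean rate = (82 × 0.53 + 41 × 0.30 + 42 × 0.265)/165 = 0.405.
- λ = Σ nᵢ(pᵢ − p̄)²/[p̄(1 − p̄)] = 2.556/0.2411 = 10.6, giving power 0.839.

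**Step 4: precision of Group 2 versus Group 3.** Half-width = 1.96 × √(p₂q₂/n₂ + p₃q₃/n₃), with p₂q₂ = 0.30 × 0.70 = 0.210 and p₃q₃ = 0.265 × 0.735 = 0.195.

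- At 55/55: 1.96 × √(0.210/55 + 0.195/55) = 0.168.
- At 41/42: 1.96 × √(0.210/41 + 0.195/42) = 0.194.

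| Reading | Evaluable, Groups 1/2/3 | Omnibus power | Half-width, Group 2 vs 3 |
|---|---|---|---|
| As sized (1:1:1) | 55/55/55 | 0.809 | 16.8 points |
| 4.1 literal | about 82/0/82 | not computable | not computable |
| 2:1:1 (assumed split) | 82/41/42 | 0.839 | 19.4 points |

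Neither reading of 4.1 gives 58/58/58.

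**The case against.** The strongest reply is that nobody would be misled. The flow chart shows randomisation into three groups, 2.4.1 names three arms, 3.2 gives each its own procedure, and the synopsis and 5.5 fix 58 per group. Three groups of 58 is 1:1:1. A single stray sentence should not override all of that, and a table that sent nobody to Group 2 would be hard to miss in a single-centre trial. Most of this stands. The intended design can be recovered, and 4.1 is not the only text that bears on allocation. What remains is that 4.1 is the only text stating a ratio, that the ratio is wrong for this trial, and that no section corrects it.

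A reader might also infer that the wording costs power. The documents do not support that. Omnibus power falls below 80% only if Group 2 is pooled with control and Group 3 receives half the patients (41/42/82, power 0.768). Section 3.2 labels Group 2 an intervention arm, which contradicts such pooling. Under the more natural pooling of Groups 2 and 3, power rises slightly. The wider interval for Group 2 versus Group 3 belongs to that 2:1:1 case only; at 41/42/82 the half-width stays at 16.8 points. No single reading shows both a loss of power and a wider interval.

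**Conclusion.** The contradiction is real and lies in the allocation specification. Taken literally, 4.1 leaves Group 2 empty and makes the three-group comparison impossible. Under an assumed equal split of the experimental half, the cost is precision for Group 2 versus Group 3 (half-width 19.4 instead of 16.8 points), with omnibus power at about 84% instead of 81%. These figures rest on the plan's own thirst rates and on 165 evaluable patients.

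Two further inferences should not be drawn. The sample size is not wrong: it reproduces at 81% power with 55 per group. Nor do the documents show that patients were, or will be, randomised incorrectly, because the REDCap table is not part of them. Since every other section is consistently three-arm, the sentence is most likely left over from a two-arm text. The correction should be made because the rule is operative and the change costs almost nothing.

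**What to change.** Replace the allocation sentence in 4.1 with wording such as: *Patients will be randomly assigned to Group 1, Group 2 or Group 3 in a 1:1:1 ratio using permuted blocks of random sizes.* Keep the block sizes undisclosed. Balanced 1:1:1 blocks are multiples of three by construction, so this need not be written down. Then check the REDCap allocation table against the new sentence and file the result.

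The cost is one sentence, one check and whatever notification 7.3 requires for the change. The total of 174, the study procedures and the planned analysis do not change.
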